Study procedures: In the past 5 years, we have documented feasibility with many of the proposed procedures in prisons (e.g., TB screening pilot using diverse diagnostic options, implementing OAT in prison, prescribing study medications, interviewing participants in private study rooms that prison constructed for us with plexiglass doors, using CASI interviews, understanding and

quantifying OAT preferences, etc). ¹⁰⁻¹⁶

Part A: All newly admitted prisoners (80-120 on admission days and all 18 years or older) undergo a complete assessment, including a brief exam and mandatory rapid HIV test by the prison medical unit. New inmates will be pre-screened, and those who meet eligibility criteria will be invited to meet with the research staff and participate in a research study where they will be screened for TB (not currently part of standard care). Inmates interested in participating will be invited to have an individual meeting with a research team member to learn more about the study. Those interested in continuing with study activities will undergo informed consent process that will cover TB screening diagnostics, study procedures, risks, and benefits. After obtaining informed consent, research staff will administer the following study activities: a brief survey, WHO symptom assessment, tuberculin skin testing (TST) with reading after 72 hours, sputum induction on 2 consecutive mornings for AFB smear, TB culture (results back 6-8 weeks using the BACTEC MGIT 960 liquid culture gold standard), and point-of care (POC) Gene Xpert. Each person will have phlebotomy for HBV and HCV Ab, LFTs, and if HIV+, CD4 testing (all of these are POC using Alere™). For those with CD4<50, they will undergo POC low-cost, urinary TB-LAM lateral flow testing (sensitivity=67%) (Alere™ Determine) to identify disseminated TB.^{17,18} Additional demographic, drug use, and TB risks will also be assessed along with prison data (release date, previous incarcerations, type of offense). Participants suspected of having active TB will then undergo CXR testing. A TB specialist will review all patients and results, ensuring that patients with suspected TB initiate treatment. All suspected or confirmed cases active TB cases in HIV+ prisoners will have ART initiated after 2 weeks of TB treatment initiation (if CNS TB not suspected) if CD4<50 and within 8 weeks for all others.

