Additionally, we will review prison logs and health records to determine how many patients are diagnosed with TB and HIV, start TB and HIV treatment, and the time to treatment initiation and completion (for TB only) among non-study patients to compare with outcomes study patients. We will abstract data from prison logs without identifiers and will not interact with incarcerated individuals other than the study participants. Additional structural non-patient data pertaining to service delivery, implementation of HIV guidelines, and operations in the prison may also be collected to compare prison HIV and TB care to national and global guidelines (ex. number of medical staff, whether diagnostic or monitoring tools (ex. HIV viral load), medications available on the prison formulary, etc) are available.

Eligibility for Part A includes:

- 1) Age \geq 18 years
- 2) Malaysian citizen
- 3) Prison sentence \geq 3 months
- 4) Absence of active TB within past 2 years of enrollment
- 5) Newly admitted prison inmate (<2 days)
- 6) Able to provide informed consent

Part B: Prisoners with LTBI from Aim 1 will be asked to participate in **Part B**. Our preliminary data suggest that >80% of all prisoners have TST+ and 94% of HIV+s and 63% of HIV-s are HCV Ab+.^{10,12,13} We have documented both in a systematic review and using empiric data in Malaysia that few prisoners with LTBI receive preventive TB therapy and for those that do, the major factor contributing to treatment non-completion is release from prison and hepatotoxicity.¹⁹ Consequently, WHO provides conflicting guidance on TB preventive therapy in prisoners. In its guidelines on managing TB in closed settings, preventive therapy is not recommended, yet in its HIV treatment guidelines, long-term isoniazid preventive therapy is recommended, especially if TST+. Since these recommendations, a large RCT among non-prisoners compared a once-weekly 12-week regimen of INH/rifapentine (12HR) to daily 26 weeks of isoniazid preventive therapy (IPT: 26H). In terms of TB prevention, efficacy was similar, but patients prescribed short-course 12HR had higher treatment completion rates (82.1% v. 69.0%; p<0.001).²⁰ Since shorter LTBI preventive strategies are likely to improve completion, perhaps overturning previous recommendations based on the best science. A remaining concern, however, is the high prevalence of PWIDs with chronic HCV infection in prison, which might increase hepatotoxicity

[figure not shown]

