in a 12HR combination since both isoniazid and rifapentine can damage the liver; CDC is calling for studies of 12HR in prisoners, but have not yet funded research. In the absence of studies of 12HR use in prisoners, it is crucial to assess both completion rates and tolerability (especially when high HCV prevalence is present).

Eligibility for Part B includes:

- 1) Meets inclusion criteria for Part A
- 2) Has latent TB (HIV+, or TST \geq 10mm (HIV-)) and no active TB disease
- 3) \geq 6 months before end of sentence to ensure option for treatment completion
- 4) AST/ALT <5 ULN, or AST/ALT <3 x ULN if TBil >2 x ULN
- 5) Not on a protease inhibitor (drug interaction with rifapentine)
- 6) No known porphyria
- 7) Not pregnant (women only).

Enrolled participants will undergo block stratified randomization, stratifying on four factors: a) CD4 <350 (if HIV+); b) HCV Ab status; c) ART status; and d) opioid dependence. After randomization and allocation to 12HR or 26H, participants will be provided 12HR weekly (12 weeks) and 26H daily (26 weeks) as directly observed therapy. Every 4 weeks, patients will be monitored for AST/ALT, adverse side effects and pregnancy. Premature treatment discontinuation will occur for any DAIDS Grade 4 toxicity, patient refusal to continue, or pregnancy (women only).

Study Design: TB Studies

Legend: LTBI=latent TB infection; H=isoniazid; HP=isoniazid + rifapentine; MMT= methadone maintenance treatment; BPN/NLX= buprenorphine/naloxone; OAT=opioid agonist treatment; ART= antiretroviral therapy; HCV= hepatitis C virus.

Part C:

A two-arm **preference trial** (no MAT, and methadone) of prisoners with opioid use disorders who are not or are currently being treated for TB and/or HIV, and are about to transition to the community and need to continue their treatment post-release. Patients may or may not be returning to Klang Valley and within 25 km of our research site. We anticipate enrolling 25-50 participants per arm.

Once consented, study participants will be provided an informed decision-making aid that will help them decide if medication-assisted treatment, specifically Methadone, is best for them. Participants will also have the option not to enroll in medication-assisted treatment.

[figure not shown]
Informed decision-making aid:

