Part A: New intakes from Kajang Prison will be recruited (80-120) per day. Mandatory HIV testing is done on all prisoners. HIV prevalence is 5%. All HIV+ prisoners upon entry will be approached for informed consent. For Part B, only prisoners who have >9 months (preferably 12 months) remaining on their prison sentence will be approached for recruitment. All subjects are expected to be Southeast Asians/Pacific Islanders. While women will represent only 10% of the sample, they will be included. The minimum age is 18 years of age, thus children 18-21 years old will be eligible for participation. Currently, only 2% of HIV+ prisoners are between 18-21 years. For part C, prisoners who have less than 90 days remaining on their prison sentence, but more than 90 days of TB treatment remaining will be approached for recruitment. They must be at least 18 years old, have latent TB infection defined by TST \geq 5mm (HIV+), or TST \geq 10mm (HIV-), return to live in Klang Valley (within 25 km of Kerinchi research site), and AST/ALT <5 X ULN.

Aim 2 will not include Human Subjects. Data analysis only.

6. Subject classification: Check off all classifications of subjects that will be specifically recruited for enrollment in the research project. Will subjects who may require additional safeguards or other considerations be enrolled in the study? If so, identify the population of subjects requiring special safeguards and provide a justification for their involvement.

 Children	 Healthy	 Fetal material, placenta, or dead fetus
 Non-English Speaking	 Prisoners	 Economically disadvantaged persons
 Decisionally Impaired	 Employees	 Pregnant women and/or fetuses
 Yale Students	 Females of childbearing potential	

NOTE: Is this research proposal designed to enroll children who are wards of the state as potential subjects? Yes No (If yes, see Instructions section VII #4 for further requirements)

7. Inclusion/Exclusion Criteria: What are the criteria used to determine subject inclusion or exclusion?

Inclusion and Exclusion Criteria:

1a: inclusion:

- Above 18 years old
- Malaysian Citizen
- Newly admitted (<2 days)
- Able to provide consent
- Absence of active TB within 2 years of enrollment

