- \geq 3 month prison sentence

1b inclusion:

- Meets inclusion criteria for part A
- Has latent TB (HIV+, or TST \geq 10mm (HIV-)) and no active TB disease
- >6 months before end of sentence to ensure option for treatment completion

- AST or ALT <5X ULN, or AST/ALT <3x ULN if TBil >2x ULN
- Not on a protease inhibitor (drug interaction with rifapentine)
- No known porphyria
- Able to provide informed consent

1c inclusion:

- Meets inclusion criteria for Part A, if possible
- Opioid dependence
- Has latent TB (HIV+, or TST \geq 10 mm (HIV-)), or active TB infection, or no TB
- Returning to live in Kuala Lumpur/Klang Valley region (within 25 km of Kerinchi research site), if possible
- AST/ALT <5X normal
- \leq 6 months remaining in prison
- Able to provide informed consent

Exclusion Criteria: Pregnant women or women planning to become pregnant will be excluded if we implement methadone or buprenorphine during pregnancy, the infant born to the mother is highly (>60%) likely to develop an infant abstinence syndrome that is avoidable by not providing MMT. If a woman becomes pregnant during the course of the study, MMT will not be discontinued if she is receiving it as withdrawal has resulted in pre-term labor. For women preferring not to be OAT, but who relapse to drug use, entry onto MMT will not be an exclusion criteria for remaining in the study.

8. How will **eligibility** be determined, and by whom?

Eligibility will be determined by the Research Assistants (RAs) hired by the University of Malaya – CERIA to work on this study. An eligibility screening form will be developed into REDCap, a data collection and management application that will be used by the local RAs.

Prior to enrollment, laboratory testing will be completed to ensure normal LFTs and urine testing will be completed to ensure that female participants are not pregnant.

9. **Risks:** Describe the reasonably foreseeable risks, including risks to subject privacy, discomforts, or inconveniences associated with subjects participating in the research.

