Part A: New intakes from Kajang Prison will be recruited daily. Mandatory HIV testing is done on all prisoners. HIV prevalence is 5%. All prisoners that meet pre-screening eligibility and who are interested in participating in the study will be approached for informed consent. For Part B, only prisoners who have >6 months (preferably 12 months) remaining on their prison sentence will be approached for recruitment. For Part C, prisoners who have less than 6 months remaining on their prison sentence will be approached for treatment.

Subjects will be recruited by local research assistants.

4. Screening Procedures

- a. Will email or telephone correspondence be used to screen potential subjects for eligibility prior to the potential subject coming to the research office? Yes No
- b. If yes, identify below all health information to be collected as part of screening and check off any of the following HIPAA identifiers to be collected and retained by the research team during this screening process.

HEALTH INFORMATION TO BE COLLECTED:

HIPAA identifiers:

- Names
- All geographic subdivisions smaller than a State, including: street address, city, county, precinct, zip codes and their equivalent geocodes, except for the initial three digits of a zip code if, according to the current publicly-available data from the Bureau of the Census: (1) the geographic unit formed by combining all zip codes with the same three initial digits contains more than 20,000 people, and (2) the initial three digits of a zip code for all such geographic units containing 20,000 or fewer people is changed to 000.
- Telephone numbers
- Fax numbers
- E-mail addresses
- Social Security numbers
- Medical record numbers
- Health plan beneficiary numbers
- Account numbers
- All elements of dates (except year) for dates related to an individual, including: birth date, admission date, discharge date, date of death, all ages over 89 and all elements of dates (including year) indicative of such age, except that such ages and elements may be aggregated into a single category of age 90 or older
- Certificate/license numbers

- Vehicle identifiers and serial numbers, including license plate numbers
- Device identifiers and serial numbers
- Web Universal Resource Locators (URLs)
- Internet Protocol (IP) address numbers
- Biometric identifiers, including finger and voice prints
- Full face photographic images and any comparable images
- Any other unique identifying numbers, characteristics, or codes

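### Part B's remaining-sentence rule is inconsistent, and at six months 26H has no slack while 12HR has about 14 weeks, so stops caused by release need their own category

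*Combined protocol and SAP*

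**What the plan says.** Four places in the current text set the remaining sentence for Part B.

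- Section V.5, Subject Population: "only prisoners who have >9 months (preferably 12 months) remaining on their prison sentence will be approached for recruitment".
- Section VII.3, Recruitment Procedures: "For Part B, only prisoners who have >6 months (preferably 12 months) remaining on their prison sentence will be approached for recruitment". This is nearly the same sentence with a different number.
- Section V.3, Part B eligibility, item 3: at least "6 months before end of sentence to ensure option for treatment completion".
- Section V.7, criteria for 1b: ">6 months before end of sentence to ensure option for treatment completion". This excludes a prisoner with exactly six months, whom Section V.3 admits.

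No section says whether the remaining sentence is counted from admission, consent, randomisation or first dose.

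On treatment, Section V.3 states that "participants will be provided 12HR weekly (12 weeks) and 26H daily (26 weeks) as directly observed therapy". The rationale for Part B in the same section reports that, among prisoners given preventive therapy, "the major factor contributing to treatment non-completion is release from prison and hepatotoxicity".

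The outcome is described in two ways. Section V.11 makes tolerability, measured by stopping study medication, the primary outcome, and stops the study if one arm's discontinuation rate is three times the other's. Section V.12 compares the proportion completing, with a bracketed condition about side effects, by intention to treat, and adds a Cox model of time to discontinuation. The reasons for premature discontinuation in Section V.3 are Grade 4 toxicity, refusal and pregnancy. Release is not listed, and no section says how a stop caused by release is to be classified.

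**The concern.** The stated purpose of the 6-month minimum is to leave room to finish treatment. It does that for 12HR. For 26H it leaves an interval equal to the course itself.

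Randomisation balances sentence length between the arms, but the same sentence affects them differently. A late start, or a week of doses to make up, can carry 26H past the release date and leaves 12HR untouched. The protocol itself names release as a leading cause of non-completion, so the route is not hypothetical.

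At stake is what the discontinuation comparison means. If a participant who leaves prison in week 25 counts as having discontinued 26H, the tolerability outcome, the Cox model and the stopping ratio all absorb sentence length as though it were intolerance. For scheduled release, the error runs in favour of 12HR.

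**Working it through.** The plan gives no figure for this point, so there is nothing to reproduce. The check compares durations and then illustrates the consequence.

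**Inputs.** Course lengths of 12 and 26 weeks (Section V.3); thresholds of 6 months (V.3, V.7, VII.3) and 9 months (V.5); 177 per arm and alpha 0.05 (V.12; two-sided assumed, since sidedness is not stated). Completion in the cited non-prison trial is 69.0% for 26H and 82.1% for 12HR (V.3; Section V.12 gives 67.0% for 26H, and 69.0% is used here). The share r of would-be 26H completers lost to release is an assumption.

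**Step 1. Slack at six months.** Slack = remaining sentence minus course length. Six calendar months are 181 to 184 days.
- 26H: 26 x 7 = 182 days, so slack is 181 - 182 = -1 to 184 - 182 = +2 days.
- 12HR: 12 x 7 = 84 days, so slack is 181 - 84 = 97 to 184 - 84 = 100 days, about 14 weeks.

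**Step 2. Slack at nine months.** 0.75 x 365.25 = 273.9 days.
- 26H: 273.9 - 182 = about 92 days.
- 12HR: 273.9 - 84 = about 190 days.

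**Step 3. A start delay, if there is one.** Section V.3 describes "TB culture (results back 6-8 weeks using the BACTEC MGIT 960 liquid culture gold standard". Suppose, and the text does not say this, that six months ran from admission and dosing waited 42 to 56 days for culture.
- 26H would be between 182 + 42 - 184 = 40 and 182 + 56 - 181 = 57 days short.
- 12HR would still have at least 181 - 56 - 84 = 41 days.
- At nine months under the same wait, 26H would keep 92 - 56 = 36 to 92 - 42 = 50 days.

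**Step 4. Illustration with no true difference.** Both arms have the same underlying completion p. 26H is observed at p x (1 - r), so the spurious gap is p x r. The last two columns give the probability of a significant result for 12HR from a two-sided test of two proportions with 177 per arm.

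| r (assumed) | Gap, p = 69% | Gap, p = 82.1% | Prob., p = 69% | Prob., p = 82.1% |
|---|---|---|---|---|
| 0% | 0 | 0 | nominal | nominal |
| 5% | 3.5 points | 4.1 points | 10% | 16% |
| 10% | 6.9 points | 8.2 points | 28% | 46% |
| 15% | 10.4 points | 12.3 points | 53% | 78% |

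**Step 5. The stopping ratio.** Non-completion stands in for discontinuation. Starting from 69.0% v 82.1%, the ratio is [1 - 0.69(1 - r)] / (1 - 0.821).
- r = 0: 0.310 / 0.179 = 1.73.
- r = 5%: 0.3445 / 0.179 = 1.92.
- r = 10%: 0.379 / 0.179 = 2.12.
- r = 15%: 0.4135 / 0.179 = 2.31.

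Release stops move the expected ratio towards 3 without reaching it over this range.

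**The case against.** **The thresholds conflict less than a count suggests.** A reader might infer that the 9-month rule is contradicted in three places. Sections V.3 and V.7 set an eligibility minimum, while V.5 and VII.3 say who will be approached. Approaching only prisoners with more than nine months is compatible with a 6-month minimum. The direct conflict is V.5 against VII.3, plus the small mismatch between V.3 and V.7 at exactly six months. This stands.

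**The delay is not established.** A reader might infer from the culture turnaround that 26H starts six to eight weeks late. The documents do not support that. The sentence criterion sits in the same list as absence of active TB, and Section VII.3 places Part B consent after latent infection has been identified. Any wait may therefore fall before the sentence is checked. No section requires culture results before Part B dosing, and Xpert, smear and specialist review are also available. This stands too, so step 3 shows a possibility only.

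**The size rests on unknowns.** A reader might assume remaining sentences uniform from 6 to 12 or 24 months and a lag of 4 to 8 weeks. That gives early release in 5% to 30% of 26H participants, and a loss of 3 to 20 points from 67% completion. The documents give neither the distribution nor the lag, and both approach rules prefer 12 months. Those figures are not evidence of size.

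**Finishing before release may be a real benefit.** Section V.3 argues that shorter regimens should improve completion. Under intention-to-treat completion, less exposure to release is arguably part of the 12HR effect, and calling it bias there goes too far. The argument does not cover tolerability, the stopping ratio, or completion qualified by side effects, because release is not an adverse reaction.

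**Some safeguards exist.** Release date is already collected (V.3, Part A), and the team reviews all discontinuations (V.11). Part C follows some people after release, but it requires opioid dependence and is not described as the continuation plan for Part B. None of this classifies a release stop.

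**Conclusion.** The concern holds for the discontinuation outcome, the stopping ratio and side-effect-qualified completion, and should be fixed. The inconsistent thresholds and missing reference date are in the text. The slack of -1 to +2 days against about 14 weeks follows from the stated durations. The direction, in favour of 12HR, holds for scheduled release; release more than about 14 weeks ahead of schedule could also cut short 12HR.

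The size cannot be computed from the documents. It is near zero if dosing starts at once and no doses are missed. The 3.5 to 12 points rest on an assumed loss of 5% to 15% of would-be 26H completers, base completion of 69% to 82%, and no completion after release. They show sensitivity and are not a forecast. The documents do not support the stronger reading that Part B's completion result is invalid. Intention-to-treat completion remains interpretable as a comparison of strategies in this setting.

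**What to change.** 1. Reconcile Sections V.3, V.5, V.7 and VII.3 to one threshold, counted from first dose, that covers 26 weeks plus time for make-up doses. The nine months already in Section V.5 leave about 92 days. The choice is the sponsor's.
2. Using the release date already collected, report release before completion as its own category, by arm.
3. State that a stop caused by release is not counted as intolerance in the tolerability outcome or in the 3-fold ratio given to the DSMB, and say how the Cox model treats it.
4. Keep intention-to-treat completion as planned, and add a sensitivity analysis that does not count release-caused stops as regimen failure. Defining this by the release date scheduled at randomisation keeps the comparison randomised. Dropping participants after they are released would not, because it would remove mainly 26H participants.

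The cost is protocol wording, one reporting category and one extra analysis. A longer threshold would shrink the recruitment pool by an amount the documents do not allow one to estimate. If Part B enrolment has closed, items 2 to 4 can still be done.

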- 6) AST or ALT $<5X$ ULN
- 7) Not pregnant (women only).

4. Genetic Testing N/A

A. Describe

- i. the types of future research to be conducted using the materials, specifying if immortalization of cell lines, whole exome or genome sequencing, genome wide association studies, or animal studies are planned
- ii. the plan for the collection of material or the conditions under which material will be received
- iii. the types of information about the donor/individual contributors that will be entered into a database
- iv. the methods to uphold confidentiality

B. What are the conditions or procedures for sharing of materials and/or distributing for future research projects?

C. Is widespread sharing of materials planned?

D. When and under what conditions will materials be stripped of all identifiers?

E. Can donor-subjects withdraw their materials at any time, and/or withdraw the identifiers that connect them to their materials?

- i. How will requests to withdraw materials be handled (e.g., material no longer identified: that is, anonymized) or material destroyed)?

F. Describe the provisions for protection of participant privacy

G. Describe the methods for the security of storage and sharing of materials

5. Subject Population: Provide a detailed description of the types of human subjects who will be recruited into this study.

For Aim 1 (a-c), only prisoners will be recruited. Community-based participants from methadone and needle/syringe sites will be recruited solely for the purpose of anonymous focus group discussions that will be used to develop the MAT decision making aid.

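### Section V.8 asks for normal liver tests, against the <5X ULN entry limit for Parts B and C; separately, the Part B bilirubin clause adds no restriction if read as a literal OR

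*Combined protocol and SAP*

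**What the plan says.** Section V.8, which explains how eligibility is determined and by whom, gives the task to research assistants using a screening form to be built in REDCap. It then says: "Prior to enrollment, laboratory testing will be completed to ensure normal LFTs". It names no Part of the study and does not define normal.

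A numeric limit appears in five places:

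- Part B, Section V.3: "AST/ALT <5 ULN, or AST/ALT <3 x ULN if TBil >2 x ULN"
- Part B, Section V.7 (list 1b): "AST or ALT <5X ULN, or AST/ALT <3x ULN if TBil >2x ULN"
- Part C, Section V.3: "AST or ALT $<5X$ ULN"
- Part C, Section V.5: "AST/ALT <5 X ULN"
- Part C, Section V.7 (list 1c): "AST/ALT <5X normal"

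The stopping rules have a similar two-level shape. Section V.10 stops medication in Parts B and C when liver tests rise above 5X ULN, or above 3X with jaundice, nausea or fatigue. Section V.9, under rifapentine, uses the same two levels and applies them if either enzyme exceeds them.

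**The concern.** These are safety-entry thresholds for two regimens that can injure the liver, and they are to be turned into form logic. Two separate wording faults can produce wrong decisions.

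First, a test required to be normal and a test required to be below 5X ULN are different entry rules. Section V.11 says Part B is there to establish safety in a population with much HCV infection, and Section V.3 reports that "94% of HIV+s and 63% of HIV-s are HCV Ab" positive. If V.8 were enforced, a prisoner with raised enzymes below 5X would be turned away although the inclusion lists admit that person. HCV-positive prisoners with raised enzymes are among those the safety aim is about.

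Second, the Part B clause joins a looser and a stricter limit with the word *or*. Read literally, the stricter limit never acts, and it is the only bilirubin rule at entry.

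A related slip is the wording *AST or ALT* in Part B (Section V.7) and Part C (Section V.3). Read literally, it asks for only one enzyme to be below the limit.

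**Working it through.** The plan gives no figure to reproduce here, so the check is one of logic.

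**Inputs.** Let m be the AST/ALT value in multiples of ULN, taking the higher of the two enzymes, and let t be total bilirubin in multiples of ULN. The limits 5, 3 and 2 come from Sections V.3 and V.7. Taking normal as m ≤ 1 is an assumption, because V.8 does not define it. Bilirubin is left out of the V.8 rule; including it would make V.8 stricter still.

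**Rules.**

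- V.8: m ≤ 1.
- Part B, literal OR: m < 5, or (m < 3 and t > 2). Every m below 3 is also below 5, so this equals m < 5.
- Part B, evident intent: m < 5, and m < 3 whenever t > 2.

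**One test case per cell.**

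| m | t | V.8 | Literal OR | Evident intent |
|---|---|---|---|---|
| 1.0 | 1.0 | in | in | in |
| 1.0 | 2.5 | in | in | in |
| 2.5 | 1.0 | out | in | in |
| 2.5 | 2.5 | out | in | in |
| 4.5 | 1.0 | out | in | in |
| 4.5 | 2.5 | out | in | **out** |
| 6.0 | 1.0 | out | out | out |
| 6.0 | 2.5 | out | out | out |
| Cells admitted | | 2 | 6 | 5 |

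V.8 and the evident Part B rule disagree in 5 − 2 = 3 cells. The literal OR and the evident rule disagree in 6 − 5 = 1 cell: AST/ALT of 3 to <5X with TBil >2X. Part C has no bilirubin clause, so its limit matches the literal OR column and differs from V.8 in 6 − 2 = 4 cells. Cells are not patients, and these counts say nothing about frequency.

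**Another literal coding.** If a programmer codes the second clause as an implication (t > 2 requires m < 3) and joins it by OR, the rule becomes looser than <5X. Anyone with t ≤ 2 then passes, even at m ≥ 5. Under neither literal coding does bilirubin restrict entry.

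**One enzyme or both.** Take ALT 6X and AST 2X. The test *AST or ALT below 5X*, read literally, is met by AST alone. The rifapentine stopping rule in Section V.9 is triggered by either enzyme above 5X, so in Part B this person would enter already above a stopping level. In Part C the same person would enter above the 5X level at which Section V.10 stops medication.

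**Which limit is intended.** Four places fit <5X and do not fit a normal-only rule:

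- Section V.9 discusses cautious rifapentine use when liver tests are abnormal.
- Part B randomization is described as "stratifying on four factors: a) CD4 <350 (if HIV+); b) HCV Ab status", followed by ART status and opioid dependence.
- Section V.12 lists baseline AST/ALT among the factors for treatment discontinuation.
- Section V.11 states the safety aim in a population with high HCV prevalence.

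The 5X/3X pairing in the stopping rules likewise shows that the bilirubin clause is meant to tighten.

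**The case against.** The strongest reply is that a sensible reader resolves both faults. V.7 is the section that sets the criteria. V.8 answers who applies them and when, in one line that sets no threshold and may use normal loosely for acceptable. Nothing says that the REDCap form will take its limits from V.8, or that the Part B clause will be coded as a literal OR. A clinician would apply the 3X limit when bilirubin is raised. This stands as an argument about likelihood and keeps the point modest. It does not remove the conflict: no text reconciles the two limits, and the people applying them are research assistants working from a form. The specialist review in Part A is described as a way to get suspected TB treated, and no liver-test entry limit is given there.

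Section V.10 also gives real cover through baseline and monthly liver tests, monthly clinical review and defined stopping levels. That cover is partial. It acts after entry and is worded for tests that rise on treatment. Between 3X and 5X it needs symptoms, not a bilirubin value.

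Two stronger readings are tempting. A reader might add the two harms together. They cannot both occur for one rule: if V.8 is enforced, the person at 3 to <5X with TBil >2X is excluded; if V.8 is set aside, the wrongful exclusions vanish. A reader might also apply the HCV prevalence to the Part B target of 354 and count people lost. The documents do not support this. They give no share of prisoners with raised enzymes, and 354 is the number to be enrolled, whereas exclusion acts on the screened pool, whose size is not given.

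**Conclusion.** The point holds as an inconsistency in safety-entry wording that should be corrected. Section V.8 conflicts with the <5X ULN limit for Parts B and C, and the <5X limit is almost certainly the one intended. The Part B bilirubin clause is meant to tighten the limit but adds no restriction if read literally.

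The consequence depends on which text is followed: wrongful exclusion above normal and below 5X under V.8, or admission of AST/ALT 3 to <5X with TBil >2X under a literal V.7. The size in people cannot be derived, because the documents give no distribution of baseline liver tests.

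A reader might infer biased treatment effects or lost power. Neither follows: both arms share the entry rule, and no stated sample size depends on it. Nor do the documents show that anyone has been wrongly screened. The conclusion rests on taking normal as no higher than 1X ULN and on the risk that form logic follows the words as written.

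**What to change.** - **Section V.8:** replace the reference to normal tests with *LFTs within the Part-specific limits in Section V.7*.
- **Part B (Sections V.3 and V.7):** write *AST and ALT both <5X ULN, and both <3X ULN if TBil >2X ULN*.
- **Part C (Sections V.3, V.5 and V.7):** write *AST and ALT both <5X ULN*, so that nobody enters with one enzyme already above the 5X stopping level.
- **REDCap eligibility form:** code exactly these rules once the clinical team has confirmed the thresholds. The eight cases in the table can serve as test cases for Part B.
- **If the form is already in use:** check past screening decisions against the corrected rules. This is possible, since the project period starts in 2016, the registry entry is described as active, and Section V.3 refers to people who have already taken part in Part A.

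The cost is a few lines of protocol text and form logic, plus a retrospective check if screening has begun. Sample size, visits and analysis do not change.
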